## Exploratory criteria

- Change from Baseline in IgE and IgG4 specific to peanut protein components at Month 3, 6 and 12 in the active Viaskin® Peanut 250 µg group versus the placebo group;
- Enumeration and characterization of reactions triggered by accidental/voluntary consumption of peanut during the study and analysis of risk-taking behaviour;
- Epigenetic modifications of the promoters of specific genes (but this will not be available at the time of database lock);
- Safety sub-analysis in subjects with mutations in the filaggrin gene versus wild type subjects;
- Sensitization status to some other allergies and their evolution over the study period;
- SCORAD evolution over time.

## 4 STATISTICAL METHODS

### 4.1 Data Quality Assurance

All tables, figures and data listings to be included in the report will be independently checked for consistency and integrity in accordance with standard PAREXEL procedures as follows:

PAREXEL Biostatistics and Statistical Programming seeks to ensure the quality of the results provided for the study in the form of Tables, Figures and Listings (TFL), and the derived datasets used in their creation, through the following processes:

- Derived datasets will be independently reprogrammed by a second programmer. The separate datasets produced by the two programmers must match 100%.
- All Tables will be independently reprogrammed by a second programmer for numeric results and must match 100%.
- Statisticians will be involved in the process of programming and validating tables that include inferential statistical results.

- Figures will be checked for consistency against corresponding tables and listings, or independently reprogrammed if there are no corresponding tables or listings.
- Listings will be checked for consistency against corresponding tables, figures, and derived datasets.
- The entire set of TFL will be checked for completeness and consistency prior to its delivery to the Sponsor by the Lead Statistical Programmer, the Lead Biostatistician, and a senior level statistician, or above, who is not a member of the project team.
- The validation process will be repeated any time TFL are redelivered using different data. Execution of this validation process will be documented through the study “Program Status Tracker” (created to track all programs for analysis variables, tables, listings and figures) that will be provided to the Sponsor at study conclusion.

## 4.2 General Considerations

The following conventions will be used when presenting summary statistics and analyzing continuous study data:

- Continuous data will be summarized in terms of number of subjects or observations with non-missing data (n), mean, standard deviation (SD), first quartile (Q1), median, third quartile (Q3), minimum (min) and maximum (max), unless otherwise stated.
- For data not normally distributed, a  $\log_{10}$  transformation will be implemented before analysis.
- Compared to the number of decimals recorded for the raw data in the database, the statistics will be reported with the following number of decimals:
  - Minimum and maximum: same number
  - Mean, median, Q1, Q3: one extra decimal
  - Standard deviation: two extra decimals.
- For any parameter at a specific visit:
  - Change from Baseline will be calculated as the value of that parameter at that visit minus the Baseline value of that parameter
  - Relative change from Baseline will be calculated as the value of that parameter at that visit minus the Baseline value of that parameter divided by the Baseline value of that parameter
- For laboratory parameters, values below a detection limit or above a specific value (e.g.  $<0.35$  kU/L or  $>100$  kU/L) will be considered as equal to that limit/value (e.g.  $=0.35$  or  $100$ ) in the statistical analyses (except in listing where the reported value will be presented).

In case of change of detection limit during the course of the study (e.g. from  $<0.35$  kU/L to  $<0.1$  kU/L), all values lower than the highest limit value will be imputed to this threshold (e.g. all values lower than  $0.35$  kU/L will be considered as equal to  $0.35$  kU/L). This conservative approach will ensure that changes from Baseline are consistent.

The following conventions will be used when presenting summary statistics for categorical study data:

- Categorical data will be summarized in terms of the number of subjects or observations providing non-missing data at the relevant time point (n), frequency counts and percentages. Any planned collapsing of categories will be detailed in the SAP text and the data displays.
- Percentages will be presented to one decimal place. Percentages will not be presented for zero counts. Percentages will be calculated using n as the denominator. If sample sizes are small, the data displays will show the percentages, but any textual report will describe frequencies only.
- Change from Baseline will be summarized using shift tables where appropriate.

The following conventions will be considered regarding study assessments and time points:

- Date and time of the first patch application will be reported in the eCRF. The baseline value is the last measurement before date and time of first patch application, in other words, Visit 4 data are taken into account for the Baseline, unless the date/time clearly indicates that the value is after the patch application. For physical exam, even if the time is not reported, V4 will be taken into account as Baseline.
- The ‘end of study’ assessment is defined as the last available post-treatment assessment.
- “Treatment Day” will be calculated relative to date of first patch application (Treatment day 1 = Date of first patch).
- Assessments collected at unscheduled visits will not be included in summary tables but only listed.
- Assessments outside of protocol allowable windows will be taken into account in the analysis according to the visit in which the data are entered.
- Early termination assessments will be analyzed as having occurred at the next scheduled assessment.

The following conventions will be considered regarding confidence p-values and confidence intervals (CI):

- P-values greater than or equal to 0.001, in general, will be presented to three decimal places. P-values less than 0.001 will be presented as “<0.001”.
- Confidence intervals will be presented to one more decimal place than the raw data.

The following conventions will be applied on diary data dates, for each incomplete patch application or removal date:

- Incomplete application date:
  - ⌘ During the first 14 days of patch application: imputed as removal dates (if removal date is complete).
  - ⌘ Beyond the first 14 days: imputed as removal date -1 (if removal date is complete).

- Incomplete removal date:
  - ⌘ During the first 14 days of patch application: imputed as application date (if application date is complete).
  - ⌘ Beyond the first 14 days: imputed as application date +1 (if application date is complete).

No imputations will be performed on time of application/removal unless explicitly described for specific analyses.

Titles for tables and listings produced will specify the type of data reported as well as the population concerned (in parentheses).

For table and/ or listings duplicated for each of the screening ED subgroup, the identification of subgroup will be mentioned left justified below the header in the core of the table as:

- Screening ED subgroup 1: Children with a screening ED of 1 mg, 3 mg or 10 mg;
- Or
- Screening ED subgroup 2: Children with a screening ED of 30 mg, 100 mg or 300 mg.

Listings will generally include the following identification variables: subject identifier, sex and age, screening ED subgroup, treatment group.

Unless specified, complete dates will be reported in listings using a DDMMYYYY format (i.e.: 01JAN2015) and time using a 24h clock-time (i.e.: 20:35).

Partial dates will be reported as MMMYYYY or YYYY.

All report outputs will be produced using SAS® version 9.3 or a later version in a secure and validated environment. Each report output will be provided to the Sponsor in a Microsoft Word document (one document per output). All report outputs will be also pooled in one single Microsoft Word document.

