#### *6.1.1.2 Time Interval and Doses*

The order of the formulas to be consumed during the first and the second day of the DBPCFC will be determined at random by the unblinded study-trained person preparing the formula using a specific randomization list provided to her/him for this purpose. Other members of the site staff (for example the Investigator, study coordinators, and study nurses), the subject/parents/guardians will remain blinded to the order of consumption until the end of the second day of the DBPCFC. Up to 7 days (1 week) between the 2 days of the DBPCFC will be permitted. The 2 days of the DBPCFC may be 2 consecutive days, but not the same day.

The challenge will consist on giving doses of peanut protein or placebo in gradually increasing doses at 30-minute intervals. This standard interval has been used safely in the past, but the Investigator may use clinical judgment to increase the intervals between doses if there is a concern that an objective reaction may be developing.

The starting dose is 1 mg of peanut protein for the entry/screening DBPCFC as well as the post-treatment DBPCFC; the maximum dose is 300 mg of peanut protein for the entry/screening DBPCFC and 2,000 mg for the post-treatment DBPCFC.

The peanut protein dose increments for the entry/screening DBPCFC are 1 mg, 3 mg, 10 mg, 30 mg, 100 mg, and 300 mg.

The entry/screening DBPCFC challenge is stopped at the 300 mg dose as a maximum, regardless of whether a reaction occurred before or not.

The peanut protein dose increments for the post-treatment DBPCFC are 1 mg, 3 mg, 10 mg, 30 mg, 100 mg, 300 mg, 1,000 mg and 2,000 mg.

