#### 7.2.4 Visit 4 (Day 1), First Day of Treatment

All screening assessments must be completed and subject eligibility must be checked before entry into the double-blind treatment period; thereafter, dates of all study visits will be scheduled relative to the date of Visit 4. Visit 4 will take place at a maximum of 42 days after Visit 1 and might occur even closer to Visit 1 provided that Visit 2 and Visit 3 have been performed in between. Ideally, it will take place 1 day after Visit 3 and it may take place up to several weeks after Visit 3, respecting the maximum interval of 42 days after Visit 1. Visit 4 may take place the same day as Visit 3 for those Investigators willing to combine the 2 visits, under the condition that all procedures of both visits and their specific durations are respected.

The following assessments will be performed at this visit:

- Physical examination (including a complete skin examination; see [Section 6.2.4](#));
- Vital signs (see [Section 6.2.3](#));
- PEF (see [Section 6.2.6](#));
- Confirm eligibility of subject and perform randomization;
- AEs recording (including volunteered or solicited AEs and AESI);
- Concomitant medications (see [Section 5.8](#));
- Dispense first box of study drug (instruct subject/parents/guardians on the proper application, timing and storage);
- Apply the first Viaskin® patch to the subject and stick the tear-off part of the pouch label in the appropriate section of the subject diary.
- Keep under observation on-site for 3 hours after the patch has been applied;
- Check skin reaction under patch and grade severity (see [Table 6](#), [Section 6.2.8](#));
- Without removing the patch, take a photograph of the site of application of the Viaskin® patch after the 3 hours of application, load it onto the PEPITES website (described in [section 6.2.8](#)) and keep it in the subject's medical records or source documents;
- Patch adhesion Investigator's assessment: Investigator assesses the adherence of the patch to the skin as well as the occlusion of the patch chamber just after first application and after 3 hours prior to discharge;
- Dispense subject diary (instruct subject/parents/guardians on the use); see [Section 6.2.7](#));
- Dispense the camera to the parents/guardians and instruct them when and how to use it;
- Dispense the subject safety leaflet and subject identification card;

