Subject diary (dispense/check)				X	X	X	X	X	X						X	X	X	X			X		X	
Dispense subject safety leaflet and subject identification card				X																				
Study drug dispensation				X					X						X									
Apply 1 Viaskin® patch at site				X																				
Check the used/unused study drug dispensed						X			X						X						X		X	
Check skin reaction under the patch and grade it 				X		X			X						X						X		X	
Photographs of the back where patches were applied				X		X			X						X						X		X	
Patch adhesion: - subject's assessment												X 	X 	X 	X 	X 	X 	X 	X 					
Patch adhesion: - Investigator's assessment				X		X			X						X						X			
Dispense epinephrine auto-injector and anaphylaxis emergency action plan				X																				
Review utilization of epinephrine auto-injector						X			X						X									

Study Assessments	Screening		Treatment Period												End of Study		Early Termination	Unscheduled Visit		
	V1	V2	V3 	V4 	PC	V5	PC	V6	PC	V7	PC	V8	PC	V9	V10	V11	V12	ET	UV 	
	D-42			D1	D4	D8	D22	M1	M2	M3	M4.5	M6	M7.5	M9	M12					
and anaphylaxis emergency action plan (when required)																				
Hours under observation before discharge		3	3	3											3	3				

Abbreviations: D = Day; DBPCFC = Double-blind, placebo-controlled food challenge; ET = Early termination; FAQLQ/FAIM = Food Allergy Quality of Life Questionnaire/Food Allergy Independent Measure; FEV1 = Forced expiratory volume in one second; M = Month; PC = Phone contact; PEF = Peak expiratory flow; SCORAD = Scoring atopic dermatitis; SPT = Skin prick test; UV = Unscheduled Visit; V = Visit.

- 1 Visit 3 within 2 weeks of V2 and through D-1. Visit 4 may take place on the same day as Visit 3, but this would result in a very long day for the subject (parents/guardians) as all Visit 4 procedures would then have to take place that same day.
- 2 Unscheduled Visit in case of AEs, need for treatment re-supply, etc. Procedures will be performed as deemed necessary by the investigator.
- 3 Except for those that depend on the results of the immunological markers testing (peanut-specific IgE) and on the outcome of the entry/screening DBPCFC.
- 4 Including history of peanut allergy.
- 5 Including a complete skin examination, body weight and height.

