- 6 These examinations are to be done before the DBPCFC. Additionally, they can be repeated during the DBPCFC procedure on both days anytime if judged necessary by the Investigator.
- 7 Blood pressure, heart rate and respiratory rate.
- 8 FEV1 will be measured in subjects 6 years of age and older.
- 9 Peanut-specific IgE, peanut-specific IgG4, peanut specific IgE and peanut specific IgG4 to Ara h 1, Ara h 2, Ara h 3, Ara h 8 and Ara h 9. IgE specific to cow's milk, egg white, house dust mites, and grass pollen will be collected at Visit 1 and Visit 10 only and in case of an early termination visit.
- 10 Laboratory tests performed centrally. Hematology: hemoglobin, hematocrit, platelets, red blood cells, white blood cells with differential cell count. Biochemistry: aspartate aminotransferase, alanine aminotransferase, total bilirubin, total protein, blood urea nitrogen, creatinine.
- 11 For both FAQLQ and FAIM, subjects ≥8 years of age will use the Child Form of the FAQLQ/FAIM. All parents/guardians will use the Parental Form for children. The specific forms of FAQLQ and FAIM will be completed in the countries where they are available in local languages.
- 12 Signing the consent for the flagrin genetic analysis can be done any time after the subject is effectively randomized in the study. However, collection of blood is recommended only once at any of the following visits: Visit 7, 8 or 10.
- 13 Check the reaction of the skin on the back of the subject and grade the severity of the local skin reactions. At Visit 4, grading is to be done before patch

- application and 30 min, 1 h, 2 h and 3 h after patch application.
- 14 The assessment of the patch adhesion to the skin will consist of a 28-day specific analysis to occur between Month 3 (Visit 7) and Month 6 (Visit 8). This assessment period can be extended up to Month 9 (Visit 9) in case it has not been completed or fully completed between Month 3 and Month 6.
  - 15 The same treatment box dispensed at visit 9 will be re-dispensed at visit 10 (until visit 11) after the compliance has been assessed

Time windows:

Visit	Time windows
V1	D-42 max before V4
V2	Anytime through D-2
V3	Within 1 weeks of V2 and through D-1
PC-D4, PC-D22	+/- 2 days
V5 (D8), V6 (M1), PC-M2	+/- 3 days
V7 to V10 (M3,6,9,12,PC M4.5, M7.5)	+/- 7 days
V11	Maximum 1 week after V10
V12	V11 + 2 weeks

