#### 4.9.7 Vital Signs

The following vital signs will be recorded, before each DBPCFC challenges and at V1 (D-42), V4 (D1), V5 (D8), V6 (M1), V7 (M3), V8 (M6), V10 (M12), End of study, Early termination visit and at any unscheduled visit:

- Systolic blood pressure (in mmHg),
- Diastolic blood pressure (in mmHg),

- Heart rate (beats/minute),
- Respiratory rate (breaths per minute).

The following results will be tabulated for all vital signs:

- Summary statistics of values by visit and changes from Baseline (V4 or V3 –if missing at V4-)
- Number and percentage of subjects with vital signs abnormalities at D-42, Baseline (D1), D8, M1, 3, 6 and 12 for heart rate, systolic blood pressure and diastolic blood pressure classified using the criteria defined below.

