#### 4.9.9 Spirometry and Peak Expiratory Flow Results

For subjects aged 6 years or older (at the date of the visit), spirometry (FEV1) will be performed at V1 (D-42), V7 (M3), V8 (M6), V9 (M9), V10 (M12), Early Termination Visit and at any unscheduled visit at the discretion of the investigator.

PEF will be performed before each DBPCFC challenge and at V1 (D-42), V4 (Baseline D1), V5 (D8), V6 (M1), V7 (M3), V8 (M6), V9 (M9), V10 (M12), Early termination visit and at any unscheduled visit at the discretion of the investigator.

The following results will be tabulated:

- Summary statistics for FEV1 value (L) and FEV1 percent predicted by visit, and change of value from Baseline (D-42) by visit,
- Summary statistics for PEF value (L) and PEF percent predicted by visit, and change of value from Baseline (D1) by visit.

All FEV1 and PEF data will be listed.

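### When Visit 4 is held on the second food-challenge day, the SAP's baseline for vital signs and PEF can be a value taken after a treated peanut reaction

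*SAP*

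**What the plan says.** **Baseline rule.** SAP 4.2 takes the last measurement before the first patch and identifies it with Visit 4: "in other words, Visit 4 data are taken into account for the Baseline". The one exception is a value whose date or time shows that it was taken after the patch. SAP 4.9.7 repeats this for vital signs, with Visit 3 only as a fallback: "Summary statistics of values by visit and changes from Baseline (V4 or V3 –if missing at V4". SAP 4.9.9 gives no fallback for PEF: "Summary statistics for PEF value (L) and PEF percent predicted by visit, and change of value from Baseline (D1) by visit". Day 1 is Visit 4.

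**Visit schedule.** Protocol 7.2.4 states: "Visit 4 may take place the same day as Visit 3 for those Investigators willing to combine the 2 visits", provided all procedures and durations of both visits are kept. Footnote 1 to SAP Table 1 agrees: "Visit 4 may take place on the same day as Visit 3, but this would result in a very long day for the subject". The SAP's table of time windows, however, places Visit 3 "Within 1 weeks of V2 and through D-1", and the heading of Protocol 7.2.3 also ends the window at Day -1.

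**Food challenge.** Visit 3 is the second challenge day (Protocol 7.2.3). On formula order, Protocol 6.1.1.2 says: "The order of the formulas to be consumed during the first and the second day of the DBPCFC will be determined at random". Visit 3 can therefore be the peanut day.

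**The concern.** The baseline rule guards against one contaminating event, the patch, and not against the other that can occur on the same day, the challenge. Every randomized child must have had objective symptoms that stopped the peanut challenge (Protocol 4.1, criterion 7), and those symptoms are treated (Protocol 6.1.1.3). The challenge symptom sheet (Protocol Appendix 6) lists tachycardia, a 10-20% fall in blood pressure and wheezing among the graded reactions. These bear directly on the variables being baselined.

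A single unsuitable baseline carries into every later change score for that child. It also enters the SAP Table 3 flags defined by change from pre-dosing, if pre-dosing there means baseline (the table does not define it). Month 12 vital signs and PEF are taken before that visit's challenge (Protocol 7.2.9), so a pre-challenge value could be compared with a post-reaction one.

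**Working it through.** **1. Can the sequence occur?** Randomization takes place at Visit 4, after screening is complete and eligibility confirmed (Protocol 4.5.3), and eligibility needs the challenge result. On a combined day, Visit 4 measurements would therefore naturally follow the challenge. This order is inferred; neither document gives clock times for Visit 4 vital signs or PEF on such a day.

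**2. Does it fit in one day?** There are six entry doses at 30-minute intervals (Protocol 6.1.1.2), so first to last dose takes 5 × 0.5 h = 2.5 h without repeats or extensions. Minimum observation after the last dose is 3 h, and observation after the first patch is 3 h. The total is 2.5 + 3 + 3 = 8.5 h, so it fits. If the challenge observation is completed first, Visit 4 measurements come about 3 h or more after the last dose.

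**3. Is an uncontaminated value available?** Yes. Visit 3 vital signs and PEF are taken before the challenge (Protocol 6.2.3, 6.2.6 and 7.2.3). PEF is not requested for children aged 4 at Visit 1, so for them only vital signs are at issue.

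**4. How many children?** The documents do not give the share c with combined visits or the formula-order ratio. Assume a 1:1 order, so that peanut falls on day 2 in half. Affected baselines = 330 × c × 0.5.

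| Assumed c | Affected children | Share of 330 |
|---|---|---|
| 0% | 0 | 0% |
| 5% | 8.25, about 8 | 2.5% |
| 10% | 16.5, about 17 | 5% |
| 20% | 33 | 10% |

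**5. What happens to a flag in an affected child?** This is an illustration. Assume a heart-rate baseline raised by s = 10 beats/min and a normally distributed between-visit change with SD 10 to 18; neither figure is in the documents. With no true change, the chance per visit of a false flag for a decrease of more than 20 is Φ((−20 + s)/SD).

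| SD | s = 0 | s = 10 |
|---|---|---|
| 10 | Φ(−2.00) = 2.3% | Φ(−1.00) = 15.9% |
| 14 | Φ(−1.43) = 7.7% | Φ(−0.71) = 23.8% |
| 18 | Φ(−1.11) = 13.3% | Φ(−0.56) = 28.9% |

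For a true increase of 30 beats/min at SD 14, the chance of exceeding the 20-beat limit is Φ((30 − s − 20)/14). This is Φ(0.71) = 76% at s = 0 and Φ(0) = 50% at s = 10.

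**6. What happens across all children?** At SD 14, the rate of false decrease flags is 7.7% + (affected share) × (23.8% − 7.7%). For affected shares of 2.5%, 5% and 10% this gives about 8.1%, 8.5% and 9.3%.

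**The case against.** The strongest reply is that this is an optional edge case which may never have arisen. Protocol 7.2.4 prefers Visit 4 one day after Visit 3, the SAP warns of the long day, and the stated Visit 3 window, read literally, rules out a shared date. A site might also postpone Visit 4 after a day-2 reaction, which would bring the affected share of combined visits below half. All of this stands: the documents show that such baselines are possible, not that any occurred.

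Two existing provisions might be said to cover the case. Protocol 8.2.2.1 defines baseline as the latest *valid* pre-dose assessment, and the blinded data review (SAP 4.4) can exclude subject data before unblinding. But *valid* is not defined for vital signs or PEF, and SAP 4.2 does not carry the word over. A general power to exclude data does not replace an explicit rule naming Visit 4. The observation of at least 3 h and the resting measurement (Protocol 6.2.3) lessen the likely shift without excluding it.

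The limits on impact also stand. The outputs are descriptive, and the absolute limits in SAP Table 3 do not depend on baseline. PEF is also reported as a value and as percent predicted by visit, with no change-based PEF flag.

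A reader might infer that a reaction-lowered PEF baseline would conceal a later fall. That goes too far: those other PEF outputs remain, and the direction of any shift after treatment is unknown. A reader might also take the drop in flags for an increase of more than 20, from 7.7% to 1.6% at SD 14 with no true change, as lost detection. It is a lower false-flag rate. The 76% to 50% comparison is the relevant one for detection.

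**Conclusion.** The concern holds in conditional form. As written, the SAP rule can select a post-reaction value when three things coincide: combined visits, peanut on the second day, and Visit 4 measurements taken after the challenge. The first is permitted, the second follows from random order, and the third is inferred from randomization requiring the challenge result.

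The size is unknown and may be zero. About 8 to 33 of 330 children are affected if 5% to 20% had combined visits and order was 1:1. Within an affected child the distortion could be material (false decrease flags rising from 2-13% to 16-29% per visit), but that rests on an assumed shift and SD. Averaged over all children, the movement is small.

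A reader might infer a biased treatment comparison. The documents do not support that: the measurement precedes treatment, so no difference between arms is expected. Efficacy is untouched, FEV1 uses the Day -42 baseline (SAP 4.9.9), and laboratory data use Visit 1 (SAP 4.9.6). This is a correction to descriptive safety outputs, worth making because it needs only data already collected.

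**What to change.** Add to SAP 4.2, 4.9.7 and 4.9.9: when Visit 3 and Visit 4 have the same date, baseline for vital signs and PEF is the pre-challenge value recorded at Visit 3; otherwise Visit 4 is kept. The rule may be limited to days on which peanut was given. State that pre-dosing in Table 3 means this baseline, and report the number of children with combined visits, split by formula on that day.

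Reconcile the Visit 3 window ending at Day -1 with the same-day permission in Protocol 7.2.4 and SAP Table 1 footnote 1.

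The cost is SAP wording and one derivation line, to be specified before unblinding. There is a small downside: the baseline visit will differ between children. Unless the rule is limited to peanut days, some clean placebo-day Visit 4 values will also be replaced by slightly earlier ones, a departure from the protocol's preference for the latest value.
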